9.10. Definition of NSAID-Inadequate Response (NSAID-IR)

For prior use of a given NSAID, the criterion of an inadequate response (NSAID-IR) can be satisfied in any one of the following three possible conditions:

1. Discontinued due to adverse event or intolerability: NSAID was taken and was discontinued due to adverse event prior to Day 1 of the study. This will be checked using Prior and Concomitant Medications NSAID CRF page where the start date and end date were before Day 1 of the study and "Adverse Event" was checked under Reason for Discontinuation;
2. Discontinued due to lack of efficacy: NSAID was taken and was discontinued due to lack of efficacy prior to Day 1 of the study with at least a 4-week (ie, 28 days) trial prior to discontinuation. This will be checked using Prior and Concomitant Medications NSAID CRF page where the start date and end date were before Day 1 of the study, the NSAID treatment duration met the minimum duration: end date - start date + 1 \geq 28 days, and "Lack of Efficacy" was checked under Reason for Discontinuation; or
3. Ongoing but with lack of efficacy: NSAID was taken and was ongoing through Day 1 of the study with at least a 4-week (ie, 28 days) trial prior to Day 1 of the study, with active AS at Screening and Day 1 (ie, Baseline). This will be checked using (a) Prior and Concomitant Medications NSAID CRF page where the start date was before Day 1, the "Ongoing?" box was checked Yes, the NSAID treatment duration met the minimum duration: date of first dose of the study (ie Day 1) - start date + 1 \geq 28 days, (b) the date of diagnosis of Ankylosing Spondylitis was present on the Primary Diagnosis CRF page at Screening visit, and (c) BASDAI score of \geq 4 and back pain score (BASDAI question 2) of \geq 4 at both Screening and Baseline (ie Day 1) visits on the BASDAI CRF page.

Multiple occurrences of the above three conditions for the same NSAID whether in different doses or different dosing frequency are counted as only one unique NSAID-IR. Based on all NSAIDs entered into the Prior and Concomitant Medications NSAID CRF page, the Primary Diagnosis CRF page (for condition 3), and the BASDAI CRF page (for condition 3) for each

subject, the number of NSAIDs-IR per this subject will be counted. A subject has to meet at least 2 NSAIDs-IR to enroll.

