4.1. Inclusion Criteria

Subjects must meet all of the following inclusion criteria to be eligible for enrollment into the study:

1. Evidence of a personally signed and dated informed consent document indicating that the subject has been informed of and is capable of comprehending all pertinent aspects of the study.
2. Willing and able to comply with scheduled visits, treatment plan, laboratory tests, and other study procedures.
3. Subject is at least 18 years old (*or* the minimum country-specific age of consent if >18) at the screening visit.
4. The subject has a diagnosis of AS based on the Modified New York Criteria for Ankylosing Spondylitis (1984). See [Appendix 2](#).
5. The subject must have a radiograph of the SI joints (AP Pelvis) documenting diagnosis of AS. Previous radiographs (up to 2 years old) can be used if they are accepted by the central reader. Otherwise, a new radiograph will be obtained during the screening period.
6. Subject has active AS Screening and Baseline (Day 1) visits defined as:
 - BASDAI score of ≥ 4 ; and
 - Back pain score (BASDAI Question 2) of ≥ 4 .
7. Subject has active disease despite nonsteroidal anti-inflammatory drug (NSAID) therapy or is intolerant to NSAIDs as defined by:

Subject must have had at least a total of 2 occurrences of an inadequate clinical response (minimum of 4 week trial) or intolerance to at least 2 different oral NSAIDs. An inadequate response to a previous NSAID or TNFi is defined as a lack of sufficient clinical response based on a clinical judgment or based on a related adverse

event (eg an adverse drug reaction requiring discontinuation) to the subject's previous treatment for AS. This will be documented on the relevant case report form (CRF).

Intolerance is defined as having discontinued NSAID treatment due to a related adverse event (eg, allergic reaction, gastrointestinal symptoms or signs, hypertension, etc).

8. Subjects who are designated as TNFi-IR must have received at least 1, but not more than 2 approved TNF inhibiting biologic agent that was administered in accordance with its labeling recommendations and was inadequately effective after the minimum treatment times listed below and/or not tolerated after one or more doses.

- At least 3 months of adalimumab treatment;
- At least 3 months of etanercept treatment;
- At least 4 infusions of infliximab;
- At least 3 injections of golimumab;
- At least 3 months of certolizumab treatment.

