5.8.2. Stable Background Pain or Other AS Therapy

Subjects taking permitted csDMARDs (eg, methotrexate (≤ 25 mg/week) or sulfasalazine (≤ 3 gm/day)), nonsteroidal anti-inflammatory drugs including selective cyclooxygenase-2 inhibitors (COX-2 inhibitors), and/or corticosteroids (≤ 10 mg prednisone mg/day) must remain on the same dose regimen throughout the study. Daily dosages of NSAIDs/COX-2 inhibitors, corticosteroids, opioids, and acetaminophen/paracetamol must be stable for 1 week prior to first study dose and must remain so during the study treatment period (Week 48) except if adjustment is needed to protect a subject's safety. Daily dosage of NSAIDs/COX-2 inhibitors, corticosteroids, opioids and acetaminophen/paracetamol must not be modified within the 24 hours prior to any study visit, except if adjustment is needed to protect a subject's safety.

Subjects using topical NSAIDs or anesthetics (ie, Ben-Gay®) on peripheral joints are allowed if stable for 1 week prior to the first study dose and must remain so during the study treatment period.

Glucosamine sulfate and chondroitin sulfate are allowed in the study but subjects should be on a stable dose for 1 week prior to first dose of investigational product and throughout the study.

The total daily dose of acetaminophen may not exceed 2.6 grams per day, and the total daily dose of opioid may not exceed the potency equivalent of 30 mg of orally-administered morphine (See [Appendix 5](#)).

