4.2.2. Deviations Assessed Prior to Randomization

Exceptions to the inclusion or exclusion criteria are not expected to occur; but any subject who fails meeting any of the following protocol inclusion criteria will be excluded from the PP analysis set.

- Subjects who failed to meet the Modified New York Criteria for Ankylosing Spondylitis (1984) at screening. The AS diagnosis at screening is recorded on the Case Report Form (CRF) page for primary diagnosis. A subject who did not have this CRF page filled out will be considered having this exclusion criterion for PP analysis set met.
- Subjects who had BASDAI score <4 or back pain score (BASDAI Question 2) <4 assessed at either screening or Baseline (ie, Day 1) visit. The BASDAI CRF pages at screening and Baseline will be used to check this condition.
- Subject who failed to meet the criteria of at least 2 NSAIDs-IR (see definition of inadequate response to NSAID in [Appendix Section 9.10](#)).
- Subjects who failed to meet the criteria of:
 - Being naïve to prior bDMARD, or
 - Having an inadequate clinical response or intolerance due to treatment-related AE to at least 1, but not more than 2 approved TNFi's (ie, 1 or 2 TNFi-IR) or having bDMARD Use (Non-IR).

[Appendix Section 9.11](#) provides more details on how to check these criteria and to derive the stratification factor.

Full lists of DMARDs and NSAIDs can be found in [Section 9.6](#).

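### SAP 9.10 leaves out the oral-route condition of inclusion criterion 7 and does not define when two NSAID entries are the same NSAID, so the per-protocol check can pass a subject who failed only one oral NSAID

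*SAP*

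**What the plan says.** Protocol 4.1, criterion 7, requires at least two occurrences of "inadequate clinical response (minimum of 4 week trial) or intolerance to at least 2 different oral NSAIDs".

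SAP 4.2.2 lists failures of inclusion criteria that remove a subject from the PP set. The NSAID item is "Subject who failed to meet the criteria of at least 2 NSAIDs-IR", with the definition left to SAP 9.10.

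SAP 9.10 accepts an NSAID as an inadequate response under any one of three conditions:

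- stopped for an adverse event or intolerability;
- stopped for lack of efficacy after at least 28 days;
- "Ongoing but with lack of efficacy: NSAID was taken and was ongoing through Day 1 of the study with at least a 4-week" trial, with an AS diagnosis date recorded and with BASDAI and back pain at 4 or above at Screening and Baseline.

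The count is "Based on all NSAIDs entered into the Prior and Concomitant Medications NSAID CRF page", together with the diagnosis and BASDAI pages for the third condition. Multiple occurrences "for the same NSAID whether in different doses or different dosing frequency are counted as only one unique NSAID-IR". The threshold is stated as "A subject has to meet at least 2 NSAIDs-IR to enroll".

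On topical products, Protocol 5.8.2 states: "Subjects using topical NSAIDs or anesthetics (ie, Ben-Gay®) on peripheral joints are allowed if stable for 1 week" before the first dose, and that use must then stay stable during treatment.

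**The concern.** The SAP rule is meant to implement criterion 7, but the word *oral* has dropped out. It appears in none of the three conditions and not in the counting paragraph. Because the protocol allows continuing topical NSAID use, the omission can change a subject's classification.

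A second, smaller gap is that 9.10 merges repeat entries of the same NSAID but names only dose and dosing frequency as differences to ignore. It is silent on salt, formulation and fixed combination.

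The PP set is there to remove subjects whose deviations could materially affect the primary efficacy result, and the sponsor chose failure of two NSAIDs as one such criterion. If the check passes subjects who do not meet it, Supportive Analysis 2 cannot show whether the ASAS20 and ASAS40 results depend on them. The baseline summary of 2 versus 3 or more NSAID inadequate responses (SAP 6.5.2) uses the same count.

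**Working it through.** The plan gives no figure to reproduce here. The check compares the rules and then applies the SAP count to constructed histories.

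**Step 1: route.** Criterion 7 restricts to oral NSAIDs. SAP 9.10 takes all NSAIDs on the CRF page. The SAP does state route where it wants it: the prior corticosteroid row in 6.5.2 is limited to oral use. No such limit is given for NSAIDs.

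**Step 2: can a topical product meet a condition?** Use under Protocol 5.8.2 must be stable before the first dose and remain so, so it will typically be ongoing at Day 1, as the third condition needs. The other parts of that condition are at least 28 days of use, an AS diagnosis, and BASDAI and back pain of at least 4 at both visits. The diagnosis and activity parts repeat inclusion criteria 4 and 6, so every eligible subject should meet them. What remains is 28 days of use. The condition asks for no separate judgment that the product itself failed.

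**Step 3: what is the same NSAID?** SAP 4.2.2 points to section 9.6 for the NSAID list. Table 7 there is arranged by WHODrug Preferred Term and has 36 NSAID terms. Grouped by first word they give 27 substances. Five substances have more than one row: diclofenac 5, dexketoprofen 3, and ibuprofen, naproxen and piroxicam 2 each. The surplus rows are 4 + 2 + 1 + 1 + 1 = 9, and 36 − 9 = 27. Section 9.10 does not say whether the unit of counting is the term or the substance.

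**Step 4: apply the count.** Every entry below is assumed to meet one of the 9.10 conditions. The threshold is 2.

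| History | By Table 7 term, any route | By substance, any route | By substance, oral only (criterion 7) |
|---|---|---|---|
| Oral naproxen + topical ketoprofen | 2 | 2 | 1 |
| Oral diclofenac sodium + topical diclofenac diethylamine | 2 | 1 | 1 |
| Oral naproxen + oral naproxen sodium | 2 | 1 | 1 |
| Oral naproxen at two doses | 1 | 1 | 1 |
| Oral naproxen + oral celecoxib | 2 | 2 | 2 |

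The first row is the firm result: the SAP count passes the subject on either reading of the same NSAID, while criterion 7 is not met. The second and third rows go wrong only if the count is made by Preferred Term. In the last two rows all counts agree.

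**The case against.** **The CRF is not shown.** The NSAID page may be limited to oral or systemic products, or may record route. Protocol 5.8.2 does not say where topical use is entered. Summaries of the requirement in the Protocol Summary, Protocol Section 3 and SAP 2.2 also omit route; only criterion 7 says oral. This stands as a limit on how often the gap matters. It does not remove the gap, because SAP 4.2.2 sets out to check the inclusion criteria and 9.10 as written has no route condition.

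**Different drugs are checked.** A reader might infer that the SAP has no different-drug check, or that one gel is enough to pass. Neither is supported. Section 9.10 counts repeat entries of one NSAID once, and a topical product supplies only one of the two responses needed. Nor does the SAP say that each Table 7 row counts separately. Section 9.10 does not cite the table, and naproxen and naproxen sodium can naturally be read as one NSAID. The salts point is an undefined term, not a missing check.

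**The rule does not err in one direction only.** It is tempting to say that it can only keep too many subjects. Criterion 7 allows inadequate response on clinical judgment, whereas 9.10 counts a stopped NSAID only if adverse event or lack of efficacy was the recorded reason. It can therefore also reject subjects who meet criterion 7.

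**Adverse events.** Criterion 7 speaks of related adverse events, while the first 9.10 condition accepts any adverse event recorded as the reason for stopping. A reader might call this a further loosening. The case is thin: recording the event as the reason for stopping that drug already implies attribution, and the documents do not show whether the CRF holds relatedness.

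**Safeguards and size.** Sites must review and document eligibility. SAP 4.2.1 lets deviations be added, with the PP list finalised before Week 16 unblinding, and SAP version 4 already revised the NSAID list after blinded review. A known violation can therefore still be excluded, although the stated algorithm would not find it.

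The numerical effect would probably be small. Suppose a share f of the PP set, balanced across arms, is wrongly kept, with treatment difference Ds against D overall. Removing them gives (D − f·Ds)/(1 − f). Take the design difference D = 20 points from Protocol 9.1 and, purely as an assumption, f = 5%. With Ds = 0 the result is 20/0.95 = 21.1 points; with Ds = 40 it is (20 − 2)/0.95 = 18.9. No document supports any particular f.

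**Conclusion.** The point holds in limited form. SAP 9.10 conflicts with the criterion it implements: without a route condition, a permitted topical NSAID ongoing for at least 28 days plus one failed oral NSAID scores 2, and the subject stays in the PP set. This assumes that topical products can appear on the NSAID CRF page, which the documents neither confirm nor exclude. The status of salts and fixed combinations is a separate ambiguity that two programmers could resolve differently.

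The reach is narrow: Supportive Analysis 2 for ASAS20 and ASAS40, and one descriptive baseline row. The FAS primary and key secondary analyses and the Type I error controlled testing do not use this count. The number of subjects affected cannot be derived from the documents, and no estimate of it should be attached to the point. It is a correction worth making because it is cheap, not because it threatens the trial's main conclusion.

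**What to change.** In SAP 9.10:

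1. State that only entries with an oral route are counted.
2. Define the same NSAID at active-substance level, so that salts, formulations and fixed combinations of one substance count once. A mapping column in Table 7, applied also to terms found in the database but not listed, would make this reproducible.
3. Use the resulting count in both 4.2.2 and 6.5.2.

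Do this before the PP list is finalised for Week 16 unblinding. If the CRF page is already restricted to oral products, a sentence saying so settles the first item.

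The cost is a few lines of SAP text and a short mapping. The PP set may become slightly smaller. No protocol change or new data collection is needed if route is already recorded. If it is not, the SAP should say how route will be established from the medication entry under blinded review.

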- All PROs should be performed before any other study procedures at the clinic visit. These include the following: ASAS/ASDAS_{CRP} Component: “Patient Global Assessment of Disease (NRS)”, “Patient Assessment of Spinal Pain” which includes Total Back Pain (NRS) and Nocturnal Spinal Pain (NRS), BASDAI (NRS), BASFI (NRS), ASQoL, SF-36v2, EQ-5D-3L and EQ-VAS, FACIT-F, - WPAI and AS-HCRU Questionnaire.
- Verify morning dose of investigational product was not administered by subject. If the dose was administered, continue with visit but re-instruct subject on the requirement for in-clinic dosing;

Note: For subjects where the visit is conducted in the afternoon or evening, verify the afternoon or evening dose of investigational product was not administered by the subject.

- Blood pressure (seated), pulse rate and temperature (via tympanic, oral or temporal, preferred);
- 12-lead electrocardiogram submitted to central reader;
- Laboratory testing: Central laboratory tests include: Hematology, Urinalysis, Chemistry Panel, Lipid Profile (fasting), Urine Pregnancy Test (for women of childbearing potential only), hsCRP;
- Blood sample for FACS Analysis;
- Complete Physical Examination: General appearance, skin (presence of rash), HEENT (head, eyes, ears, nose and throat), lungs (auscultation), heart (auscultation for presence of murmurs, gallops, rubs), lower extremities (presence of peripheral edema), abdominal (palpation and auscultation), neurologic (mental status, station, gait, reflexes, motor and sensory function, coordination) and lymph nodes;

- Weight (without shoes preferred);
- Specific Medical History: History of uveitis, psoriasis, inflammatory bowel disease and peripheral articular involvement as assessed by swollen joint count;
- BASMI (linear function) by qualified blinded assessor: Lateral spinal flexion, tragus-to-wall distance, lumbar flexion (modified Schober), maximal intermalleolar distance and cervical rotation;
- Spinal mobility obtained by qualified blinded assessor: chest expansion;
- Assessment of swollen joints (44-joint count) by qualified blinded assessor;
- Assessment of enthesitis using the MASES Index by qualified blinded assessor; Complete drug accountability;
- Monitoring of adverse events and concomitant treatments. Record any modifications, deletions or additions;
- Contraception check: Confirm and document that proper contraception is being used;

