3.4.1. Stratification Factor

Subjects will be stratified by prior treatment history (strata of "bDMARD-naïve" and "TNFi-IR or bDMARD Use [Non-IR]") at randomization. The stratum derived from data collected on prior medications taken and on the reasons for their discontinuation in the clinical database will be used for analysis. Specifically, prior medications taken before Day 1 collected on the Prior and Concomitant Medications DMARD CRF pages (bDMARDs subcategory) will be used to derive the strata. An inadequate response to a medication is defined when its discontinuation was due to either adverse event or lack of efficacy (see [Appendix Section 9.11](#) for additional details to derive this stratification factor). For the primary endpoint of ASAS20 at Week 16 and the key secondary endpoint of ASAS40 at Week 16 only, a sensitivity analysis may need to be performed using the stratum from the randomization system (if there are differences between that from the randomization system and that derived from the clinical database) (see [Section 6.1.2](#) and [Section 6.2](#)).

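### The SAP's check for an ongoing NSAID (9.10, condition 3) accepts no end date on or after Day 1, so an NSAID stopped after randomisation can fall out of the baseline count and wrongly remove a subject from the per-protocol set

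*SAP*

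**What the plan says.** SAP 9.10 gives three ways in which a prior NSAID can count as an inadequate response. The first two concern NSAIDs already stopped. For an adverse event the check is "where the start date and end date were before Day 1 of the study and 'Adverse Event' was checked under Reason for Discontinuation". For lack of efficacy it is "where the start date and end date were before Day 1 of the study, the NSAID treatment duration met the minimum duration", with that reason ticked.

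The third concerns an NSAID still in use at entry. In words it is "NSAID was taken and was ongoing through Day 1 of the study with at least a 4-week (ie, 28 days) trial prior to Day 1", with active disease at Screening and Day 1. The check on the Prior and Concomitant Medications NSAID page is "where the start date was before Day 1, the 'Ongoing?' box was checked Yes, the NSAID treatment duration met the minimum duration", where duration runs from the start date to Day 1 and must be at least 28 days. Several qualifying occurrences of one NSAID at different doses or frequencies count once.

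The count is used in two places. SAP 4.2.2, under deviations assessed before randomisation, removes from the per-protocol set any "Subject who failed to meet the criteria of at least 2 NSAIDs-IR". SAP 6.5.2 tabulates the number of prior NSAID inadequate responses as 2 or as 3 and more.

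On NSAID use during the trial, Protocol 5.8.2 says that daily doses "must remain so during the study treatment period (Week 48) except if adjustment is needed to protect" the subject's safety. Protocol 5.8 requires stop dates for concomitant medications. From Week 2 onward the visit procedures (for example Protocol 6.2.2 and 6.2.6) include "Monitoring of adverse events and concomitant treatments. Record any modifications, deletions or additions". SAP 4.2.1 fixes the per-protocol exclusion list shortly before unblinding for the Week 16 analysis.

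**The concern.** The definition of condition 3 looks only at the period up to Day 1, as does Protocol 4.1, inclusion criterion 7. The check adds a requirement that neither contains: that the record is still marked as ongoing. If the box follows the current state of the record, a subject's pre-randomisation status is decided partly by what happens after randomisation.

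At stake is the per-protocol analysis. An eligible subject can be excluded as if an entry criterion had been broken. Because the trigger comes after randomisation, such exclusions need not be balanced between the arms, and a per-protocol set is meant to avoid exactly that kind of selection in its entry criteria. The baseline table would also undercount, and it has no cell for a subject whose count is 1.

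**Working it through.** The plan gives no figure to reproduce, so the check consists of applying the rule to constructed histories.

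**Inputs.** Conditions 1 to 3 come from SAP 9.10 and the threshold of two from SAP 4.2.2. The box is treated as Yes only while the record has no end date; this is an assumption, because the CRF is not available.

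- NSAID A was stopped for lack of efficacy well before Day 1, with a start on study day −300 and an end on day −200. Duration = −200 − (−300) + 1 = 101 days, which is at least 28. A counts under condition 2 in every scenario.
- NSAID B was started 101 days before Day 1. Duration by the condition 3 formula = 101 + 1 = 102 days, which is at least 28. B was in use on Day 1, so it meets condition 3 as defined in words.
- In a second run, a third NSAID, C, also qualifies under condition 2.

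**Check as written.** Condition 3 holds if start < Day 1, box = Yes and duration ≥ 28.

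**Check as amended.** Condition 3 holds if start < Day 1, (box = Yes or end ≥ Day 1) and duration ≥ 28.

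| What happens to B | A + B: as written | A + B: amended | A + B + C: as written | A + B + C: amended |
|---|---|---|---|---|
| Still ongoing | 2 (kept) | 2 (kept) | 3 (kept) | 3 (kept) |
| Stopped on Day 1 | 1 (excluded) | 2 (kept) | 2 (kept) | 3 (kept) |
| Stopped on Day 40, adverse event | 1 (excluded) | 2 (kept) | 2 (kept) | 3 (kept) |
| Stopped on Day 40, lack of efficacy | 1 (excluded) | 2 (kept) | 2 (kept) | 3 (kept) |
| Closed on Day 40, re-entered at a new dose on Day 41 | 1 (excluded) | 2 (kept) | 2 (kept) | 3 (kept) |
| Replaced by another NSAID on Day 41 | 1 (excluded) | 2 (kept) | 2 (kept) | 3 (kept) |

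The reason is the same in every row after the first. B's end date is not before Day 1, so conditions 1 and 2 fail. B is no longer ongoing, so condition 3 fails. A record that starts on Day 41 cannot help, because its start is not before Day 1.

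Two things follow. The loss of one count occurs whenever B has an end date on or after Day 1. The loss of the subject occurs only when B was one of exactly two qualifying NSAIDs; with three, the subject stays in the per-protocol set but moves from the higher to the lower category of the baseline table.

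If the box instead records status at Day 1 and is never updated, every scenario gives 2 (or 3 with C), and the written check does no harm.

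**The case against.** The strongest objection is that the CRF is not in the documents. Nothing says when the box is read or whether a later stop overwrites it. Section 9.10 speaks of prior use, measures duration to Day 1 and ends with a condition for enrolment, and 4.2.2 places the check before randomisation, so the intention is plainly Day 1 status. That stands as a qualifier on the effect. It does not remove the point: the page covers concomitant as well as prior medication, stop dates are recorded during the trial, and the list is fixed after those entries exist. A programmer following the text would exclude the subject.

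A second objection is that NSAID doses must stay unchanged to Week 48 except for safety, and that rescue is confined to other analgesics (Protocol 5.8.3, Appendix 6). Changes should therefore be uncommon, and the documents show no difference between arms. This stands too. Differential exclusion is a possibility, not a finding.

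Some stronger readings are tempting but not supported:

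- A reader might put a number on it. Assuming that 40–60% of subjects need an ongoing NSAID to reach two, and that 5–15% of those stop or change it, gives 0.40 × 0.05 = 2% to 0.60 × 0.15 = 9% of 240, about 5 to 22 subjects. Neither input has any basis in the documents. The effect on a response rate is equally open. With an assumed 68/120 = 56.7% on tofacitinib, losing five responders gives 63/115 = 54.8%, but losing three responders and two non-responders gives 65/115 = 56.5%.
- A reader might infer that a dose change shortly before Day 1 resets the 28 days. The SAP tests the duration of NSAID treatment and does not say that it is computed per dose record.
- A reader might extend the point to the stratification factor, since SAP 9.11 checks biologic-naïve status by the absence of any entry. SAP 3.4.1 already limits that derivation to "prior medications taken before Day 1 collected on the Prior and Concomitant Medications DMARD CRF pages", and 9.11 itself defines naïve status as of Day 1.

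**Conclusion.** The point holds in a limited form. As written, the condition 3 check does not match its own definition, and an NSAID used through Day 1 with a later end date satisfies none of the three checks. This rests on the page being a running log. For a dose change, it also rests on the change closing the old record; the sentence on different doses of one NSAID suggests this but does not state it.

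The consequence is confined to Supportive Analysis 2 for ASAS20 and ASAS40 (SAP 6.1.2 and 6.2) and to the baseline count in SAP 6.5.2. The primary and key secondary analyses use the full analysis set, which does not depend on this count, so they and the testing hierarchy are untouched. The number of subjects affected is unknown and may be small. The case for correcting the rule is that a stated derivation can misclassify eligible subjects on a post-randomisation event, and that correcting it is nearly free.

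**What to change.** In SAP 9.10, condition 3(a), replace the requirement that the 'Ongoing?' box be Yes with: 'Ongoing?' = Yes, or end date on or after Day 1. Leave the start-date, 28-day and active-disease requirements as they are. The existing rule that one NSAID counts once already prevents double counting when a dose change creates a second record. If the CRF in fact captures status at Day 1 only, a sentence saying so would serve instead.

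The cost is one clause in the SAP and one line of the derivation, using dates already collected. Because it touches neither the primary endpoint nor its analysis, it does not meet the condition in Protocol Section 9 for a protocol amendment. It should be done while blinded, before the per-protocol list is finalised for the Week 16 analysis.
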